## Chapter 4: Statistical Analysis Plan

The sample size calculations for all Specific Aims were performed using PASS 2005 (Hintze J, 2007) software using  $\alpha = 0.05$  and  $\beta = 0.20$  (power =80%) and then combined to determine the optimal sample size to address all of the aims. Estimates of sample size were computed for each specific aim, as follows:

**Specific Aim 1:** To test whether the combined treatment of 0.01% atropine and soft bifocal contact lens wear produces slower myopia progression and axial elongation compared to soft bifocal contact lenses alone over 3 years.

For Aim 1, the sample size is driven by the desired difference in spherical equivalent progression between the two groups. This difference needs to be of a magnitude that is considered clinically relevant. [name] and colleagues showed that the mean ( $\pm$  SD) myopia progression of single vision soft contact lens wearers was  $-1.29 \text{ D} \pm 0.71$  over three years ([name] et al. 2008). The proposed myopia progression in the +2.50 D add soft bifocal group for the sample size calculation of the BLINK Study based on a treatment effect of 50% was  $-0.65 \text{ D}$ . A reasonable reduction in myopia progression from the addition of atropine to the +2.50 D add bifocal lenses would be about  $0.33 \text{ D}$ , an additional reduction of 50%. Using a standard deviation of  $0.71 \text{ D}$  and taking into account the pair-matched design, the sample size for this aim would be 39 subjects per group.

**Specific Aim 2:** To test whether early changes in choroidal thickness can be used as predictors of long-term myopia progression / axial elongation.

For Aim 2, the correlation between choroidal thickness and refractive error / axial length ranges from 0.35 to 0.74 based on previous studies (Nishida et al. 2012; Flores-Moreno et al. 2013; Vincent et al. 2013). A sample size of 44 per group will allow for detecting a correlation of 0.41 between short-term changes in choroidal thickness and long-term myopia progression / axial elongation.

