To test these hypotheses, I will enroll 52 myopic children aged 7 to 11 years into a treatment protocol of wearing soft bifocal contact lenses in combination with daily administration of one drop of 0.01% atropine for three years. The rates of myopia progression and axial elongation will be compared to the rates in age-matched subjects who are receiving treatment with only soft bifocal contact lenses in the Bifocal Lenses In Nearsighted Kids (BLINK) Study (U10EY023208). The BLINK Study is a multi-center, randomized clinical trial chaired by my primary mentor, and it was designed to test the hypothesis that the peripheral myopic defocus produced by the add power of soft bifocal contact lenses is responsible for slowing myopic eye growth.

**Aim 1. To test whether the combined treatment of 0.01% atropine and soft bifocal contact lens wear produces slower myopia progression and axial elongation compared to soft bifocal contact lenses alone over 3 years.** I will compare the three-year change in spherical equivalent refractive error and axial length of subjects undergoing the combined treatment to age-matched subjects wearing only soft bifocal contact lenses in the BLINK Study.

**Aim 2. To test whether early changes in choroidal thickness can be used as predictors of long-term myopia progression / axial elongation.** I will measure the change in choroidal thickness from baseline to 3 weeks in the subjects receiving combination treatment and in the BLINK Study subjects using soft bifocal contact lenses alone. I will then determine whether the amount of 3-week change in choroidal thickness correlates with the 3-year rate of myopia progression / axial elongation in each group.

**Scientific & Clinical Impact:** The results of this study will have significant implications for future studies to develop and test new therapeutic regimes that optimize the effect of myopia control through combined pharmacological and optical interventions. The outcomes will also aid in understanding the potential role of short-term changes of choroidal thickness in long-term regulation of myopia progression and ocular growth.

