### Chapter 3: Study Design

This proposed experiment is an ancillary study of a multi-center, randomized clinical trial Bifocal Lenses In Nearsighted Kids (BLINK) Study (U10EY023208), which compares myopia progression rate between subjects wearing single vision contact lenses and those wearing soft bifocal contact lenses. The BLINK Study will enroll 294 myopic children aged 7 to 11 years at two clinical centers: The Ohio State University (OSU) College of Optometry and The University of Houston College of Optometry (UHCO).

The subjects in the BLINK Study will be randomly assigned to wear either single vision soft contact lenses or soft bifocal contact lenses with either a +1.50 D add or +2.50 D add power for at least three years, with 49 subjects in each treatment arm at each clinical center. This proposed study will recruit one group of 52 additional subjects that meet BLINK eligibility criteria and that are age-matched with a comparison group -- 49 BLINK study participants who are wearing soft bifocal contact lenses with +2.50 D add power.

The subjects in this proposed study will wear soft bifocal contact lenses in combination with daily administration of 0.01% atropine for three years. The rates of myopia progression and axial elongation will be compared to those in the comparison group in the BLINK Study. The protocol for the outcome measures in this proposed project is consistent with the BLINK Study.

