### Sample Size Conclusion

Using the maximum required sample size (39 subjects for aim 1, and 44 for aim 2) and adjusting for 18% loss to follow-up gives a total sample required of **52**.

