## Chapter 5: Eligibility

In order to participate in the study, all subjects must meet the following criteria at Visit 1:

Age at baseline examination	7 to 11 years of age, inclusive
Spherical component of refraction	-0.75 to -5.00 D in each eye, inclusive, cycloplegic autorefraction
Astigmatism	≤1.00 DC in each eye, cycloplegic autorefraction
Anisometropia	≤2.00 D, based on spherical component
Best-corrected visual acuity (VA)	+0.1 logMAR or better in each eye at distance
VA with bifocal contact lens	+0.1 logMAR or better OU with +2.50 D add bifocal contact lenses at distance and near
Contact lens fit	The +2.50 D add soft bifocal contact lens must provide adequate movement and centration for continual wear
Compliance with atropine	Finish at least 85% of 0.01% atropine during the run-in period (see description in text)
History of vision correction	By patient report, not more than one month of gas permeable, soft bifocal, or corneal reshaping contact lens wear.
Myopia control	By patient report, not more than one month of participation in myopia control with treatments including, but not limited to, soft bifocal or orthokeratology contact lenses, atropine, bifocal spectacles
Ocular health	No eye diseases or binocular vision problems that may affect vision or contact lens wear (e.g. strabismus, amblyopia, etc.)
Ocular surgery	No previous intraocular or corneal surgery
Systemic health	No systemic diseases that may affect vision, vision development, or contact lens wear (e.g. diabetes, Down's syndrome, etc.)
Medications	No chronic use of medications that may affect immunity, such as topical or systemic use of corticosteroids
Participation	Agree to participate in the study for three years

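### Aim 1's 39 per group at 80% power rests on an unstated within-pair correlation of about 0.5, for which age-matching gives no stated basis

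*Combined protocol and SAP*

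**What the plan says.** Chapter 4 (Specific Aim 1) sets alpha at 0.05 and power at 80%. It reports from a cited study that the "myopia progression of single vision soft contact lens wearers was" -1.29 D over three years, with an SD of 0.71 D. "The proposed myopia progression in the +2.50 D add soft bifocal group for the sample size calculation of the BLINK Study" is given as -0.65 D, and adding atropine is taken to reduce it by about a further 0.33 D. With an SD of 0.71 D and "taking into account the pair-matched design, the sample size for this aim would be 39 subjects per group".

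Chapter 4 does not state whether the test is one- or two-sided, what within-pair correlation was assumed, or what SD of pair differences was entered.

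The matching is described only by age. Chapter 2 (Aim 1) speaks of "age-matched subjects wearing only soft bifocal contact lenses in the BLINK Study", and Chapter 3 says the new subjects are "age-matched with a comparison group -- 49 BLINK study participants" wearing the +2.50 D add. Eligible ages are "7 to 11 years of age, inclusive" (Chapter 5).

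The Sample Size Conclusion takes the larger requirement, 44 from Aim 2, and "adjusting for 18% loss to follow-up gives a total sample required of" 52. Chapter 2 adds that finding no advantage for the combination would point to saturation of the shared mechanism.

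**The concern.** A paired calculation needs the SD of the difference between the two children in a pair. The only SD in the plan describes variation from child to child. The two are equal only if matched children's three-year progressions correlate at 0.5. If the true correlation is lower and the other inputs stand, the study has less than the stated 80% chance of detecting the 0.33 D benefit it was designed around.

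The consequence goes beyond the power statement. Chapter 2 attaches a mechanistic reading to a null result and offers no way to tell saturation from low power. A null result in an underpowered comparison could then be reported as evidence about the pathway.

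**Working it through.** **Inputs from Chapter 4.** Difference 0.33 D; SD 0.71 D; alpha 0.05; power 80%. Sidedness is not stated. Every rho below, and every SD other than 0.71 D, is an assumption.

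**Formulas.** SD of pair difference = SD × √(2(1 − rho)). Paired power comes from the noncentral t distribution with n − 1 degrees of freedom and noncentrality 0.33 × √n / (SD of pair difference). Unpaired power uses n1 + n2 − 2 degrees of freedom and noncentrality 0.33 / (SD × √(1/n1 + 1/n2)).

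**Step 1: reproduce 39.** Two-sided paired test with 0.71 D as the SD of the pair difference: 38 pairs give 79.7% and 39 give 80.7%, so the requirement is 39. The other calculations that use 0.71 D directly do not return 39: a one-sided paired test needs 31 pairs, and an unpaired test needs 73 per group two-sided or 58 one-sided.

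**Step 2: what this implies.** Setting SD × √(2(1 − rho)) = SD gives 2(1 − rho) = 1, so rho = 0.5. The smallest rho that gives 80% with 39 pairs, two-sided, is 0.49.

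**Step 3: is this reading certain?** No. A one-sided test with a per-child SD of 0.71 D and rho of about 0.35 also returns 39. Either route needs a substantial within-pair correlation that the plan does not state.

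**Step 4: power with a per-child SD of 0.71 D, two-sided, 39 pairs.**

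| rho | SD of pair difference (D) | Power | Pairs needed for 80% |
|---|---|---|---|
| 0 | 1.00 | 52% | 75 |
| 0.1 | 0.95 | 56% | 68 |
| 0.2 | 0.90 | 61% | 61 |
| 0.3 | 0.84 | 67% | 53 |
| 0.4 | 0.78 | 73% | 46 |
| 0.5 | 0.71 | 81% | 39 |

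**Step 5: numbers likely to be analysed.** The new group leaves 52 × 0.82 = 42.6 children. If the comparison group also loses 18% (an assumption), it leaves 49 × 0.82 = 40.2. About 40 pairs give 53% to 68% at rho 0 to 0.3. An unpaired 42 vs 40 gives 55%, with a detectable difference of about 0.44 D at 80% power.

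**Step 6: conditions that narrow or close the gap.**
- One-sided at SD 0.71 D, 39 pairs, rho 0 to 0.3: 64% to 78%.
- Unpaired 42 vs 40, two-sided: 69% at SD 0.60 D, 77% at 0.55 D and 84% at 0.50 D.

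**The case against.** The strongest reply is that low power has not been shown. The shortfall needs three things together that the documents do not settle: a per-child SD of 0.71 D in the treated groups, a two-sided test, and a rho well below 0.5. The 0.71 D comes from single-vision wearers with a mean of -1.29 D, whereas the groups compared are projected at -0.65 D and about -0.32 D and may well vary less. Aim 1 is also worded directionally. All of this stands, and it is why the shortfall is stated as conditional. It does not rescue the 80% as written, because Chapter 4 itself uses 0.71 D and states none of the other conditions.

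Three stronger readings are tempting and should be resisted.

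- **That 39 is an arithmetic error.** It is not; it follows exactly from a recognisable calculation.
- **That age cannot produce a correlation near 0.5 in children of 7 to 11.** The documents give no progression by age. The only variance quoted comes from a different population than the projected bifocal mean, so a value of 0.49 cannot be ruled out. What can be said is that no basis for it is given.
- **In the plan's favour, that the 44 required by Aim 2 covers Aim 1.** At SD 0.71 D, two-sided, 44 pairs would still need rho 0.42 for 80%. With 18% loss among the 49 comparison children, only about 40 would remain to form pairs.

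It is also fair that Chapter 2's remark on saturation is hedged rationale and not a decision rule. It is still the only guidance the plan gives on reading a null result.

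**Conclusion.** The concern holds as a matter of an undocumented and unsupported input. The 80% for Aim 1 depends on a pair-difference SD that the plan's own between-child SD does not supply without a correlation of about 0.5. That 0.71 D was entered as a two-sided pair-difference SD is inferred from the match to 39; the plan does not say so.

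If the per-child SD is 0.71 D, the test is two-sided and rho is 0 to 0.3, a true 0.33 D benefit would be missed in 33% to 48% of studies with 39 pairs. A reader might infer that Aim 1 is simply underpowered. The documents do not support that, because they fix neither rho, nor sidedness, nor the SD in bifocal wearers, and an SD of 0.50 D would give adequate power without any benefit from matching. The point should be fixed. It does not by itself call for a larger study.

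**What to change.** **Chapter 4.** State the sidedness and the pair-difference SD that was used. Replace the unqualified 80% for Aim 1 with power, or detectable difference, over a stated range of rho (for example 0 to 0.5) and per-child SD (for example 0.50 to 0.71 D). Calculate it at the number of pairs expected after loss in both groups.

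**Chapter 2.** Commit to reporting the 95% confidence interval for the added benefit, and do not treat a non-significant result by itself as evidence of saturation. If the result is non-significant and the interval still includes 0.33 D, call it inconclusive. This label should not apply to significant results, whose intervals may also include 0.33 D.

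**Cost.** Wording in two chapters and no extra subjects. The price is a less favourable power statement and a weaker reading of a null result.

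### Aim 2 names no covariate for its within-group correlation in children aged 7 to 11, so it cannot show that early choroidal change predicts progression beyond age

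*Combined protocol and SAP*

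**What the plan says.** Chapter 2 (Aim 2) plans to determine whether the 3-week change in choroidal thickness "correlates with the 3-year rate of myopia progression / axial elongation in each group". Chapter 4 (Specific Aim 2) supplies the only statistical detail: "A sample size of 44 per group will allow for detecting a correlation of 0.41 between short-term changes in choroidal thickness and long-term myopia progression". It places 0.41 within a published range: "the correlation between choroidal thickness and refractive error / axial length ranges from 0.35 to 0.74 based on previous studies". Neither chapter names a covariate, a partial correlation or a regression for this aim, and age is not mentioned in connection with it.

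Age appears in two other roles. Chapter 5 sets it as an eligibility range, "7 to 11 years of age, inclusive". Chapters 2 and 3 use it to match the recruited children to the comparison group: Aim 1 is to "compare the three-year change in spherical equivalent refractive error and axial length of subjects undergoing the combined treatment to age-matched subjects", and the recruits are to be "age-matched with a comparison group -- 49 BLINK study participants". The matching enters the statistics only in the Aim 1 sample size: "taking into account the pair-matched design, the sample size for this aim would be 39 subjects per group".

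**The concern.** The Aim 2 correlation is computed inside each group. Matching on age makes the two groups alike in age, but each still spans five years of age, and nothing in the stated Aim 2 method takes that spread out. Two different things can follow, depending on whether the early choroidal response itself varies with age.

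- If it does, age can create an apparent association. If the two age correlations have opposite signs, age can hide a real one.
- If it does not, age-related spread in progression acts only as noise and lowers the crude correlation.

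These are alternatives, not joint effects. What is at stake is interpretation. Aim 2 speaks of predictors, and Chapters 1 and 2 argue that both treatments act along a pathway through the choroid. A crude correlation shows that choroidal change and progression go together. It does not show that the choroid adds to what the child's age at Visit 1 already tells, and it does not separate a choroidal pathway from age.

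**Working it through.** **Inputs from Chapter 4:** alpha 0.05, power 80%, r = 0.41, n = 44 per group. Sidedness is not stated. Two-sided is used because it reproduces the stated size; one-sided would need only 36.

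**Step 1. The plan's own figure.** Fisher z: n = ((1.960 + 0.842) / atanh(r))² + 3. With atanh(0.41) = 0.4356, n = (2.802 / 0.4356)² + 3 = 44.4. Power at n = 44 is 79.7% by Fisher z and 80.6% by simulating the t test of r. The stated 44 reproduces.

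**Step 2. Association through age alone (assumed age correlations).** If choroidal change has no link with progression beyond age, crude r = r(choroid, age) × r(progression, age). The chance of p < 0.05 follows from atanh(r) × √(44 − 3) compared with ±1.960.

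| Age correlation with both | Crude r | Significant at n = 44 |
|---|---|---|
| 0.3 | 0.09 | 8.9% |
| 0.4 | 0.16 | 17.8% |
| 0.5 | 0.25 | 37.3% |

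To produce 0.41 from age alone would take about 0.64 with both variables (0.64² = 0.41). A sample r of about 0.30 is already significant at n = 44.

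**Step 3. Age as noise only (age unrelated to choroidal change, assumed).** Adjusted r = 0.41 / √(1 − R²), where R² is the share of progression variance that age explains. Fisher z uses n − 3 − k for k covariates. With k = 2, the second covariate is assumed to explain nothing further.

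| R² | Adjusted r | Power, k = 1 | Power, k = 2 |
|---|---|---|---|
| 0.1 | 0.432 | 83.3% | 82.4% |
| 0.2 | 0.458 | 87.9% | 87.1% |
| 0.3 | 0.490 | 92.4% | 91.7% |

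**Step 4. Price of adjusting if the covariates explain nothing.** For a partial r of 0.41 at n = 44, power is 79.7% with no covariate, 78.7% with one and 77.6% with two.

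**Step 5. Power of the adjusted test if part of the crude 0.41 is age.** With the same age correlation a for both variables, partial r = (0.41 − a²) / (1 − a²).

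- a = 0.3: (0.41 − 0.09) / 0.91 = 0.35; power with one covariate 64%; 63 per group needed for 80%.
- a = 0.5: (0.41 − 0.25) / 0.75 = 0.21; power 28%; 172 per group needed.

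**The case against.** The strongest reply is that Chapter 4 is sample-size reasoning, not a model specification. It is silent on covariates for Aim 2 but does not exclude them, and the quoted sentence is arithmetically sound. That is fair. The gap is an analysis left unadjusted by omission, not a wrong figure or a declared choice against adjustment.

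Second, Aim 2 asks whether choroidal change correlates with progression, and a crude correlation answers that. This stands for prediction in the weak sense. It does not stretch to prediction beyond age or to the choroidal pathway.

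Third, every age correlation above is assumed, and nothing in the documents shows that the early choroidal response varies with age. This stands too; at more modest values, such as 0.2 and 0.4, the rate in Step 2 is 8%.

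Fourth, Step 5 shows that adjustment can leave Aim 2 well short of 80% power. That is correct and has to be stated in the plan. But power falls there because the association beyond age is smaller, so the shortfall reflects confounding and is not a cost created by adjusting.

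Two stronger readings are tempting. A reader might infer that the plan treats age as the driver of progression. It nowhere says so; matching shows only that age was thought worth balancing. A reader might also work back from Aim 1: a paired t test with 0.33 D and 0.71 D as the SD of differences gives 38.3, hence 39. If 0.71 D is also the SD of individual progression, this implies a within-pair correlation of 0.5, so that age would explain about half the variance. The documents do not say how the pairing entered the calculation, so 39 cannot serve as evidence of the strength of age.

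**Conclusion.** The point holds as a gap in the Aim 2 analysis that is cheap to close. As written, Aim 2 can show association within each group. It cannot support a claim that choroidal change adds to age, or that the choroid is the pathway.

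The size is conditional. In one case (choroidal change varies with age and adds nothing beyond it; age correlations 0.3 to 0.5), 9% to 37% of tests are significant instead of 5%. In the other (age unrelated to choroidal change and explaining 10% to 30% of progression variance), the plan forgoes a rise in power from 80% to about 82–92% with two covariates. The documents do not say which case applies, and the two should not be added together. In the second case the plan still has its stated power for the crude r of 0.41, so what is lost is an available gain in efficiency.

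**What to change.** In Chapter 4, prespecify for each group a regression (or the equivalent partial correlation) of three-year change on the Visit 2 to Visit 3 change in choroidal thickness. Table 6-2 schedules the first choroidal measurement at Visit 2. Adjust for baseline age and baseline spherical equivalent, replacing the latter with baseline axial length when elongation is the outcome. Report the R-squared that choroidal change adds over these covariates, next to the planned crude correlation. State that any claim of prediction beyond age, or of a choroidal pathway, rests on the adjusted estimate.

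Keep 44 per group and r = 0.41, but say that the 80% power applies to the unadjusted correlation and that the adjusted test has less if age accounts for part of it (Step 5).

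The cost is wording plus two degrees of freedom per group. Age, cycloplegic autorefraction and axial length are all obtained at Visit 1, so no new measurement is needed.

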### Sample Size Conclusion

Using the maximum required sample size (39 subjects for aim 1, and 44 for aim 2) and adjusting for 18% loss to follow-up gives a total sample required of **52**.

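### Enrolling 52 does not keep the 44 evaluable children that Aim 2 needs at the plan's own 18% loss; 44/0.82 gives 54

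*Combined protocol and SAP*

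**What the plan says.** Chapter 4 sizes the two aims separately at a 5% significance level and 80% power. For Aim 1, "the sample size for this aim would be 39 subjects per group". For Aim 2, "A sample size of 44 per group will allow for detecting a correlation of 0.41"; the correlation meant is that of the early choroidal change with later progression or elongation. The Sample Size Conclusion then takes the larger of the two, opening with the words "Using the maximum required sample size (39 subjects for aim 1, and 44 for aim 2". Its result is 52, which it introduces as follows: "adjusting for 18% loss to follow-up gives a total sample required of". No inflation formula is given.

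The conclusion calls 52 a total, but the other chapters show that it is the size of the one newly recruited group. Chapter 2 states "I will enroll 52 myopic children aged 7 to 11 years into a treatment protocol" and Chapter 3 states "This proposed study will recruit one group of 52 additional subjects". The comparison children come from the BLINK trial. Chapter 3 describes them as "49 BLINK study participants who are wearing soft bifocal contact lenses with +2.50 D add power".

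**The concern.** Aim 2 correlates the 3-week choroidal change with the 3-year rate of progression or elongation within each group (Chapter 2). A child without 3-year data does not supply the planned outcome, so the 44 has to be a count of children who finish. The plan treats it that way too, since it applies the loss adjustment to 44.

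The enrolment must therefore still leave 44 after 18% of those enrolled are lost. The figure of 52 looks as if 18% of the required number had been added on, which is a different and smaller correction. At stake is whether the enrolment target, repeated in three chapters, delivers the Aim 2 number that it is said to protect.

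**Working it through.** **Inputs.** Required evaluable number: 44 per group for Aim 2 and 39 per group for Aim 1 (Chapter 4). Loss to follow-up: 18% (Sample Size Conclusion). Recruited group: 52 (Chapters 2, 3 and 4). Detectable correlation 0.41, alpha 0.05, power 80% (Chapter 4). The plan does not say whether the test is one- or two-sided; two-sided is inferred below.

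**1. The 44 itself.** By Fisher's z, n = ((1.960 + 0.842)/atanh(0.41))² + 3 = 44.4 two-sided, against 35.6 one-sided. So 44 matches a two-sided test and has no slack built in.

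**2. The plan's 52.** Adding 18% of the requirement gives 44 × (1 + 0.18) = 51.92, which rounds up to 52. This origin is inferred from the match.

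**3. The number needed.** Enrolment N must satisfy N × (1 − 0.18) ≥ 44, so N ≥ 44/0.82 = 53.66, that is 54.

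| Enrolled | Expected to finish at 18% loss |
|---|---|
| 52 | 52 × 0.82 = 42.64 |
| 53 | 53 × 0.82 = 43.46 |
| 54 | 54 × 0.82 = 44.28 |

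The largest loss at which 52 still leaves 44 is 1 − 44/52 = 15.4%.

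**4. Effect on Aim 2 power (two-sided 5%, true correlation 0.41).**

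| Evaluable n | Fisher z, bias-corrected, t-based critical value | Plain Fisher z | Simulation (400,000 runs each) |
|---|---|---|---|
| 44 | 80.4% | 79.7% | 80.6% |
| 43 | 79.5% | 78.7% | 79.7% |
| 42 | 78.5% | 77.6% | 78.6% |

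At the expected 42.64, the first method gives 79.1% and plain Fisher z gives 78.3%. The correlation detectable with 80% power is 0.408 at 44, 0.412 at 43 and 0.417 at 42 by the first method. By plain Fisher z it is 0.412 at 44 and 0.421 at 42.

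**5. Aim 1.** 39/0.82 = 47.6, so 48 would be enough, and 52 keeps 39 up to a loss of 1 − 39/52 = 25%. This counts the recruited group only, not intact matched pairs.

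**6. Comparison group (missing detail, separate from the arithmetic above).** The Aim 2 requirement is 44 in each group, and no loss rate is stated for the BLINK participants. If the 49 in Chapter 3 are the whole comparison group, they leave 44 only when loss is at most 1 − 44/49 = 10.2%. Under assumed rates, 5% loss leaves about 47 (83% power at 0.41), 10% leaves 44 (80%) and 18% leaves about 40 (76%).

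**The case against.** The strongest reply is that this hardly matters. The gap is two enrolments and about one point of power, and the choice of approximation moves power by nearly as much. Under plain Fisher z, even the plan's 44 gives 79.7%, and the 44.3 expected from 54 gives 79.9%, so neither strictly reaches 80%. By the bias-corrected method the detectable correlation at 42.64 is 0.414, which still rounds to the plan's 0.41. The target is itself soft, because Chapter 4 cites earlier correlations from 0.35 to 0.74. Retention may also beat 18%: enrolment follows a run-in period, a child who returns for the final visit does not count as lost (Chapter 7, Discontinuation), and travel may be paid for families who move.

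All of that stands as an argument about weight and sets minor as the ceiling. It does not make 52 right. The plan chose 18% with those retention measures in place and states that 52 allows for it.

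Two narrower objections also stand in part. First, Aim 1 is sized on a pair-matched design, so the reassurance there covers only the recruited-group count. Second, the 49 may not bound the Aim 2 comparison group. Chapter 3 gives 49 per arm at each of two centres, hence 98 in the +2.50 D arm, and Chapter 2 refers for Aim 2 to the choroidal change "in the BLINK Study subjects using soft bifocal contact lenses alone" without naming an add power or centre. The comparison-group figures are therefore conditional and are not part of the error.

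**Conclusion.** The concern holds as a minor arithmetic error. At 18% loss, 52 enrolled leaves an expected 42.6 evaluable children in the recruited group against the 44 required; the number that protects 44 is 54. The shortfall at 52 follows whatever formula produced it.

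The cost is about one percentage point of Aim 2 power, to roughly 78–79% at a correlation of 0.41. No analysis is affected.

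The conclusion assumes that 18% is a proportion of those enrolled and that the 44 need 3-year data. The power figures also assume a two-sided test.

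**What to change.** **Cheaper option.** Keep 52 and add one sentence to the Sample Size Conclusion: at 18% loss, about 43 of the recruited children are expected to be evaluable for Aim 2, giving power of about 78–79% at a correlation of 0.41 (detectable correlation 0.41–0.42). Name the approximation used. This is enough to settle the point.

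**Alternative.** Change 52 to 54 in the Sample Size Conclusion, Chapter 2 and Chapter 3. The cost is two more enrolments.

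**Optional.** Add one sentence giving the loss rate assumed for the BLINK comparison group, which participants form that group for Aim 2, and the evaluable number that results.
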